8.3.4 TIME PERIOD AND FREQUENCY FOR EVENT ASSESSMENT AND FOLLOW-UP

The study investigators will assess and record all events with start dates occurring any time after informed consent is obtained until Day 90 – the last visit. The study investigator will review EHR daily to collect and assess all AEs (including SAEs) from the time participants provided consent to the study until Day 10 and again during Day 30 and Day 90 follow-up visits regardless of its relationship to study drug. At each visit, the investigator will inquire about the occurrence of any new and the prognosis of already documented AE/SAEs since the last visit. All AEs will be captured in detail and followed to satisfactory resolution or stabilization, until the investigator deems the event chronic or not clinically significant and until the participant is considered to be stable. The participants will receive standard of care for the events. Site investigators will also assess if there is a reasonable possibility that the study drug or procedure caused the event. Investigators will also consider if the event is explained by the participant's underlying medical conditions, anticipated clinical course, previous medical conditions, and concomitant medications.

Routine and safety laboratory values from the respective hospital laboratories will be reported by each site investigator to the SAC as soon as the results are available to the study database. Participants will receive standard of care for the event and followed to satisfactory resolution or stabilization, The DCC will review laboratory results for completeness. Any abnormal laboratory test results (clinical chemistry, hematology, or urinalysis) or other safety assessment (e.g., CPK), including those that worsen from the baseline, felt to be clinically significant in the medical and scientific judgement of the investigator, will be recorded as AEs. The SAC will review AEs weekly and SAEs on a daily basis and any events that the clinical centers categorize as requiring treatment discontinuation for safety reasons.

The following laboratory results will be flagged as expected study AEs in this trial:

- Thrombocytopenia: Platelet count >25% reduction from the baseline;
- Liver function test abnormalities: AST, ALT, total bilirubin, alkaline phosphatase > 4 times the upper limit of normal;
- Creatinine phosphokinase (CPK): > 4 times upper limit of normal;

The following symptoms will be flagged as expected study AEs in this trial:

- Bruising
- Bleeding
- Severe diarrhea
- Severe nausea
- Flushing
- Hives
- Heartburn.

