A dose escalation study was performed in 8 healthy subjects in a non-randomized, open-label pharmacokinetics (PK) study with 250 mg NR orally administered on days 1 and 2, then uptitrated to peak dose of 1000 mg twice daily on days 7 and 8. No clinically significant changes were seen at NR dose up to 1000 mg orally twice daily in any of the five pre-specified safety endpoints, i.e., potassium, creatine phosphokinase (CPK), glucose, uric acid and alanine aminotransferase. Serum potassium decreased by an average of 0.4 mEq/L, which was statistically significant (p = 0.015) but the individual levels remain in normal range. There was a slight though statistically significant decrease for hematocrit (mean difference = -2%, p = 0.005), hemoglobin (-0.4 g/dL, p = 0.04), and platelet count (-20,000/µL, p = 0.03). There were no significant changes in blood pressure, body temperature, body weight, white blood cell count, lactate dehydrogenase or aspartate aminotransferase. In addition, there were no significant changes in serum levels of sodium, chloride, urea nitrogen, creatinine, or in white blood cell differential [38].

In an investigator-initiated randomized, placebo-controlled, double-blinded study of 40 healthy men with BMI> 30 kg/m² NR was administered at a dose of 1000mg twice daily for 12 weeks [39]. Adverse events (AEs) were reported in 4 subjects in the NR group which included pruritis, excessive sweating, bloating and transient changes in stool. There were two AEs in the placebo group which were acid reflux and loose stools. The severity was mild in all cases. Laboratory analysis for blood counts and chemistries at 6 weeks revealed no abnormalities in the NR group.

A recent report evaluated a combination of NR with an anti-oxidant pterostilbene (PT; NRPT) in 24 hospitalized patients with AKI with a single dose ranging from 250mg NR, 500mg NR, 750mg NR to 1000mg NR twice a day [15]. Compared to the baseline timepoint, NRPT dose 500 mg/100 mg twice a day increased whole blood NAD+ levels 47% at 48 h, (p = 0.04). Whole blood NAD+ levels in patients with AKI receiving placebo decreased by 50% at 48 h (p = 0.05). Compared to placebo, there was no significant difference in creatinine, estimated glomerular filtration rate (eGFR), electrolytes (sodium, potassium), liver enzymes (ALT, AST, ALP), hemoglobin, white blood count or platelet count in patients treated with NRPT at 48 h. NRPT

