There are paucity of data regarding the safety profile of NR in patients with CKD. Two clinical trials of NR in patients with eGFR 20-60 mL/min/1.73m2 are ongoing [41, 42]. Forms of vitamin B3 nicotinic acid (pyridine-3-carboxylic acid or niacin) and its circulating amide derivative nicotinamide (pyridine-3-carboxamide, NAM) have been tested in advanced CKD patients undergoing hemo- and peritoneal dialysis patients [43]. One randomized, placebo-controlled clinical trial tested NAM (750 mg twice daily) alone and in combination with lanthanum carbonate among individuals with eGFR 20-45 ml/min per 1.73 m² for 12 months [44]. This study reported severe nausea, severe diarrhea, flushing, hives, bruising and bleeding in the NAM group (n=51) which were not significantly different than that reported in the placebo group with the exception of hives. It is important to note that this particular study did not find any evidence of thrombocytopenia (platelet count <100,000/mm²), liver function abnormalities, and elevated CPK (>800 U/L) in the NAM group compared to the placebo group [44]. In patients with hemodialysis, the documented safety profile of NAM included primarily flushing, pruritus, hypotension, hepatotoxicity, and gastrointestinal upset. Most studies reported NAM associated transient thrombocytopenia without any bleeding events in hemodialysis patients which returned to normal range within weeks of discontinuation of intervention [43, 45, 46]. In contrast, studies conducted in peritoneal dialysis patients did not report such hematologic changes associated with

NAM [47]. It should be noted that NR does not induce prostaglandin-mediated flushing or vasodilatory responses [48]. One study tested NAM 100 mg twice daily for 6 months in pediatric population (age 7-17 yrs) with hyperphosphatemia undergoing maintenance hemodialysis [49]. NAM group reported diarrhea, nausea, vomiting, and flushing which were not significantly different from the control group and did not result in withdrawal from the study. Despite a significant decline in mean platelet count from the baseline in the NAM group, the platelet level remained within the normal range and none of the participants experienced any bleeding disorder.

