N-methyl-2-pyridone-5-carboxamide or 2PY, a major metabolite of NAM, is considered a uremic toxic in patients with impaired renal function [50, 51]. While serum 2PY level may increase significantly with NAM supplementation [46], the intracellular concentration may not rise compared to baseline in hemodialysis patients [52]. In general, available data conclude that NAM is safe and tolerable in adults at doses of below 3 g/day [53]. Taken together the available safety data of niacin and NAM indicate that in patients with impaired renal function both agents are tolerable [54-56]. The prominent side effects of NAM at therapeutic doses (i.e., 1000 mg/day) are gastrointestinal symptoms (mainly diarrhea) that generally resolve on treatment withdrawal or discontinuation. Develeopement of hetatoxicity require massive dose of NAM – 9 g/day and prolong therapy for months may cause thromobocytopenia [55, 56]. Based on the available data, the known potential risks of NR can be divided into those that are likely and those that are rare.

Likely

These risks are expected to occur in 5-15 participants or less out of 100 participants.

- Gastrointestinal disorders: nausea, heart burn (e.g., indigestion, gas, upper abdominal discomfort, and bloating), diarrhea, transient changes in stool;
- Musculoskeletal disorders: back soreness, muscle soreness;
- Skin disorders: pruritus, flushing, hives;
- Other disorders: leg cramps, increased bruising, excessive sweating;
- Laboratory findings: liver function abnormalities; decrease in blood urea nitrogen;

Rare

The following risk may occur at an unknown rate:

- Hematologic profile e.g., <10% reduction in hemoglobin and platelet counts
- Allergic reaction or hypersensitivity

There is no available data on potential interactions between NR and standard treatment for comorbidities (concurrent medications) or any investigational agents for the treatment of COVID-19. Administering NR concurrently with other agents may lead to antagonism or synergy or may have no effect.

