5.2 EXCLUSION CRITERIA

An individual who meets any of the following criteria will be excluded from participation in this study:

- 1. Hypersensitivity to nicotinamide riboside (NR);
- 2. Pregnant or lactating women confirmed with positive laboratory pregnancy tests as per local requirements;
- eGFR <15 mL/min/1.73 m² as per the Chronic Kidney Disease Epidemiology Collaboration equation at admission lab;
- 4. Maintenance renal replacement therapy or initiation of renal replacement therapy before randomization
- 5. Currently on NR or nicotinamide or vitamin B3 (niacin) supplementation (multivitamins are allowed);
- 6. Concomitant cirrhosis of liver or acute liver failure;
- 7. Any medical history or condition that might, in the opinion of the attending physician, put the participant at significant risk if he/she were to participate in the trial;
- 8. Individuals with kidney transplant;
- 9. Individuals with blood platelet count <100,000/microL;

Rationale: The exclusion criteria are primarily designed for patient safety. In addition, these exclusion criteria address some uncertainties in the COVID-19 severity and effects of concomitant medications on disease progression. For example, the incidence of AKI in kidney transplant recipients with COVID-19 is not well studied [73]. Moreover, kidney transplant recipients are on maintenance immunosuppressive therapy with deleterious effects on infection

outcomes. An optimal management of immunosuppressive agents in this patient group with COVID-19 is not clear [74].

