8.3.3.3 EXPECTEDNESS

The study investigators will be responsible for determining whether an AE is expected or unexpected. An AE will be considered unexpected if the nature, severity, or frequency of the event is not consistent with the risk information previously described for the study intervention and hospital course.

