8.3.5 ADVERSE EVENT REPORTING

Information on all AEs will be recorded on the appropriate eCRF. All related and relevant signs, symptoms, and results of diagnostic procedures performed because of an AE will be grouped together and recorded as a single diagnosis. AEs and SAEs related to COVID-19 outcomes or expected AEs with NR or study procedures will not be reported to sIRB and not adjudicated by SAC. Any baseline medical condition and laboratory results that are present at the time that the participant consented to the study but do not deteriorate will not be reported as an AE. However, if the medical condition deteriorates and any laboratory results become abnormal at any time during the study, these will be reported as AEs. Unexpected AEs and their relatedness to study drug or procedure will be reported.

Aggregate analyses of adverse events observed from the NIRAVA trial will detail new information regarding the investigational product NR (i.e. new side effects or increasing frequency of side effects) will be reported to SAC on weekly basis. Significant non-clinical findings will also be reported to SAC if they are suggestive of increased risk for study patricians.

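### The protocol gives incompatible rules on whether a serious, NR-related event on the Section 8.3.4 expected list goes to the SAC and can be a SUSAR

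*Combined protocol and SAP*

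**What the plan says.** Section 8.3.4 lists laboratory results and symptoms to be flagged as expected events. The laboratory entries are "Thrombocytopenia: Platelet count >25% reduction from the baseline", liver tests above 4 times the upper limit of normal (ULN), and "Creatinine phosphokinase (CPK): > 4 times upper limit of normal". The symptom entries include bleeding. Diarrhea and nausea are qualified as severe; bleeding carries no grade. No entry has an upper limit.

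The NR risk list in Section 2.3.1 gives, at an unknown rate, "Hematologic profile e.g., <10% reduction in hemoglobin and platelet counts". It also names increased bruising and liver function abnormalities, but not bleeding or CPK elevation. Section 8.3.6, under outcomes exempt from serious event reporting, attributes platelet falls above 25% to previous NR studies.

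Section 8.3.5 attaches a consequence to the label: "expected AEs with NR or study procedures will not be reported to sIRB and not adjudicated by SAC". Expectedness itself is defined more than once. Section 8.3.3.3 says: "An AE will be considered unexpected if the nature, severity, or frequency of the event is not consistent with the risk information previously described". Section 8.3.2 defines a SUSAR by inconsistency with the risks set out in the protocol. Section 8.3.6 calls an event unexpected when the protocol does not list it, and reserves SUSAR status for unexpected suspected reactions.

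**The concern.** The label is applied to platelet falls larger than any that Section 2.3.1 describes for NR, and to two kinds of event that its NR risk list does not contain. If Sections 8.3.4 to 8.3.6 are followed literally, being on the list is enough to make an event expected, however severe it is. Platelets and CPK are also signals that the trial monitors specifically.

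The stake is case-level oversight of a serious event judged related to NR. SUSAR classification and the 7-day rule for fatal or life-threatening reactions in Section 8.4.2 both require the event to be unexpected. The ad hoc unblinded DSMB review in Section 2.3.3 is triggered when a SAC member sees a pattern of unexpected events or serious events. A label that is too broad could weaken each of these.

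**Working it through.** The plan gives no figure to reproduce. The check is a reading of the sections side by side, with some arithmetic on the platelet numbers.

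**Step 1. Is the flagged platelet fall within the NR experience described?** Inputs: the mean fall of 20,000/µL in the NR pharmacokinetic study (Section 2.3.1), and the eligibility floor set by excluding "Individuals with blood platelet count <100,000/microL" (Section 5.2).

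- Baseline at which 20,000/µL is a 25% fall: 20,000 / 0.25 = 80,000/µL, below the floor.
- Size of that fall at the floor: 20,000 / 100,000 = 20%.
- Baseline above which it is less than 10%: 20,000 / 0.10 = 200,000/µL.

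The reported mean fall would not reach 25% at any eligible baseline. Individual falls can exceed a mean, so this does not show that falls above 25% cannot occur. It shows that the NR figures in Section 2.3.1 do not support calling them expected, and that Section 8.3.6 conflicts with Section 2.3.1 in attributing them to previous NR studies.

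**Step 2. Each listed item against the risk list and the routes back to review.**

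| Flagged item | NR risk list, Section 2.3.1 | Discontinuation criterion, Section 7.2 | Named example in Section 8.3.6 whose exemption lapses if related or uncertain |
|---|---|---|---|
| Platelet fall >25% | Reduction below 10% | Only if the count is <75,000/microL | Yes |
| CPK >4x ULN | Not listed | Yes, if no other cause is found | No |
| Bleeding | Not listed (bruising is) | No | No |
| Liver tests >4x ULN | Listed, no degree given | Yes, if no other cause is found | Yes, for AST and ALT |

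The Section 7.2 column matters because Section 8.3.4 has the SAC review events that lead to discontinuation for safety. For platelets that route is partial. A 25% fall from the floor leaves 0.75 x 100,000 = 75,000/microL, exactly the criterion. A 60% fall (an illustration) stays above it from any baseline over 75,000 / 0.40 = 187,500/microL.

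**Step 3. The rules applied to one case: a serious, NR-related bleed with a large platelet fall.**

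| Question | Rule | Section | Answer |
|---|---|---|---|
| Unexpected? | Not listed in the protocol | 8.3.6 | No, so not a SUSAR |
| Unexpected? | Inconsistent with the outlined risks | 8.3.2 | Can be a SUSAR |
| Unexpected? | Nature, severity or frequency inconsistent with described risk | 8.3.3.3 | Yes |
| Who decides? | Investigators / blinded SAC | 8.3.3.3 / 8.3.6 | Two answers |
| SAC adjudicates? | Not if expected | 8.3.5 | No, on one reading |
| SAC adjudicates? | SAC is alerted to unexpected events | 8.3.7 | Depends on the label |
| SAC adjudicates? | Every reportable event, serious ones included | 10.1.6 | Yes, if reportable |
| SAC sees it? | Weekly review of events, daily review of serious events | 8.3.4 | Yes |

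The same case gets opposite answers on SUSAR status and on adjudication.

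**The case against.** The strongest reply is that the protocol has several independent routes to review and that its better rules already cover the serious case. Much of this stands.

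- A reader might infer that a serious, related bleed with a large platelet fall would simply not be a SUSAR. The documents do not support that as a settled outcome: two of the three expectedness statements (Sections 8.3.2 and 8.3.3.3) leave it eligible.
- Section 10.1.6 notifies the site SAC member of every serious event at once, whatever its expectedness. Section 8.3.4 sends laboratory values to the SAC. Section 8.3.6 sends serious, treatment-related events to the DSMB and NIDDK within 7 working days. Section 8.3.5 gives the SAC weekly aggregate analyses.
- The exemption sentence in Section 8.3.5 is ambiguous. On one natural reading, serious events are exempt only when tied to COVID-19 outcomes, and the NR limb covers non-serious events.
- A reader might also infer that all three flagged laboratory items are mislabelled. Section 2.3.1 lists liver function abnormalities for NR, so that entry has a basis.
- CPK has some background basis: Section 8.2 cites elevation in about 14% of COVID-19 patients in one study, and Section 8.3.3.3 counts the hospital course.
- Section 2.3.1 is not silent on platelets and bleeding with nicotinamide, and the below-10% figure is only an example. It says nothing about CPK or bleeding.

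These points do not remove the conflict. The relatedness override in Section 8.3.6 restores reporting but does not make a listed event unexpected under that section's own test. Disease background should not settle expectedness for an event judged related to NR. Nicotinamide is a different compound, and its hemodialysis data are described thus: "Most studies reported NAM associated transient thrombocytopenia without any bleeding events in hemodialysis patients". Section 10.1.6 follows its broad statement with one about unexpected adverse events and SAEs being reported to the SAC.

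**Conclusion.** The concern holds as an internal contradiction. A serious, NR-related event on the Section 8.3.4 list can escape SAC adjudication and SUSAR status, or receive both, depending on which section a site follows. The gap is clearest for bleeding, which is named in neither the Section 7.2 criteria nor the Section 8.3.6 examples; that second list is illustrative, so the omission is not conclusive. It is narrower for platelet falls and unexplained CPK rises, which have partial routes back. Liver tests are not affected in the same way.

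The size cannot be stated in events, because the documents give no expected rate for these events in this population. The ratio of the two platelet cut-points, 25 / 10 = 2.5, might be read as a measure of the gap. It compares a flagging threshold with an example in a risk description and counts no missed cases. Platelet falls above 25% are also part of the primary safety endpoint as the synopsis defines it, so they are still collected for comparison between arms. What is uncertain is case-level review and classification.

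The conclusion rests on the text alone and assumes that no operating document outside the protocol already resolves the conflict.

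**What to change.** Reconcile Sections 2.3.1, 8.3.2, 8.3.3.3, 8.3.4 to 8.3.7 and 10.1.6:

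- Adopt one definition of expectedness that counts severity against the risks described for NR in Section 2.3.1, and have Sections 8.3.4 to 8.3.6 refer to it. State who makes the determination.
- Resolve the conflict between the below-10% platelet statement in Section 2.3.1 and the above-25% figure that Section 8.3.6 attributes to previous NR studies.
- State that the Section 8.3.4 flag does not by itself remove a serious event judged related, or of uncertain relationship, to NR from SAC adjudication or SUSAR classification.
- Reword the Section 8.3.5 exemption so that its reach over serious events is clear.

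Routine SAC review of every flagged laboratory value is not needed. The cost is wording in these sections and some additional reviews by the existing SAC; their number cannot be estimated from the documents. No dose or discontinuation rule has to change.

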8.3.5 ADVERSE EVENT REPORTING

Information on all AEs will be recorded on the appropriate eCRF. All related and relevant signs, symptoms, and results of diagnostic procedures performed because of an AE will be grouped together and recorded as a single diagnosis. AEs and SAEs related to COVID-19 outcomes or expected AEs with NR or study procedures will not be reported to sIRB and not adjudicated by SAC. Any baseline medical condition and laboratory results that are present at the time that the participant consented to the study but do not deteriorate will not be reported as an AE. However, if the medical condition deteriorates and any laboratory results become abnormal at any time during the study, these will be reported as AEs. Unexpected AEs and their relatedness to study drug or procedure will be reported.

Aggregate analyses of adverse events observed from the NIRAVA trial will detail new information regarding the investigational product NR (i.e. new side effects or increasing frequency of side effects) will be reported to SAC on weekly basis. Significant non-clinical findings will also be reported to SAC if they are suggestive of increased risk for study patricians.

8.3.6 SERIOUS ADVERSE EVENT REPORTING

The study investigators will report all unexpected serious adverse events and their relatedness to study drug or procedure to the DCC within 24 hours of awareness or initial assessment. The DCC will then notify the sIRB and NIDDK. These reporting will follow the criteria outlined in 21 CFR 312.32(c). The SAC will be blinded to the randomization code and will determine if the event is unexpected and define the relationship to NR based on section 8.3.3.2. An adverse event is considered "unexpected" if it is not listed in the study protocol (21 CFR 312.32(a)). If a determination is made that a serious adverse event which is not exempt and has a reasonable possibility of having been caused by a study procedure or the study drug, it will be classified as a suspected adverse reaction. If the suspected adverse reaction is unexpected, it will be classified as a SUSAR.

The DCC will report all unexpected deaths, serious and treatment related adverse events, and SUSARs to the DSMB and NIDDK within 7 working days after receipt of the report from a

clinical site. A written report will be sent to the DSMB, FDA, local IRB, and the sIRB within 15 calendar days. The DSMB will also review all reported adverse events and clinical outcomes during scheduled DSMB meetings. The DCC will distribute the written summary of the DSMB's periodic review of reported adverse events to the local IRB and sIRB in accordance with NIH guidelines (*http://grants.nih.gov/grants/guide/notice-files/not99-107.html*).

In addition, (1) serious, unexpected suspected adverse reactions, (2) findings from other clinical, animal, or in-vitro studies that suggest significant human risk, and (3) a clinically important increase in the rate of a serious suspected adverse reaction will be reported to all investigators, sIRB, local IRB, the FDA, and the DSMB no later than 15 calendar days after determining that the information qualifies for reporting [21 CFR 312.32(c)(1)].

Clinical Outcomes that will be Exempt from Serious Adverse Event Reporting

Pre-specified laboratory safety endpoints will be designated to evaluate possible laboratory abnormalities that might be seen with NR based on previous studies with NR (i.e., <10% reduction in hemoglobin and >25% reduction in platelet counts from baseline).

Study-specific outcomes of COVID-19 infection and critical illness will be systematically collected for all participants in both study group and are exempt from adverse event reporting unless the investigator considers the event to be Definitely or Possibly Related (or of an Uncertain Relationship – section 8.3.3.2) to the study drug or study procedures. Examples of study-specific clinical outcomes include:

- Death not related to the study procedures
- Cardiovascular events
 - Receipt of vasopressors
 - Atrial or ventricular arrhythmia
 - Cardiac arrest
 - Respiratory events
 - Hypoxemia requiring supplemental oxygen
 - o Acute respiratory distress syndrome
 - Receipt of mechanical ventilation
 - Receipt of extra-corporeal membrane oxygenation
- Gastrointestinal events
 - Elevation of aspartate aminotransferase or alanine aminotransferase
 - Acute pancreatitis
 - Severe diarrhea
- Hematological events
 - o Anemia

o Thrombocytopenia

Note: A study-specific clinical outcome may also qualify as a reportable adverse event.

